The results of this comparison can only be fully understood if both variables (sex and gel) are controlled for. Thus, controls will include dosing and sampling in the absence of sex (both Groups) or in the absence of gel (Group 1 only). In all cases, clinical samples will be obtained ~2 hours after sex or a matched timepoint (no sex). Mucosal secretions have “endogenous” antiviral activity, which likely reflects the cumulative effects of antimicrobial peptides, pH, and other mucosal mediators. The physical act of intercourse may alter this activity, reflecting contributions from semen and/or its impact on the female genital tract. Thus, CVL obtained at the Screening visit (no gel/no sex) and the Enrollment Visit, where no gel will be applied, but sex will occur,) for Group 1 participants will provide baseline data in the absence of any gel product (See Section 7 for additional details). If tenofovir retains its antiviral activity following sex, then the anti-HIV activity in the CVL sample collected at the Gel/Sex Visit should be comparable to that of a sample collected at the Gel/No Sex Visit and should be greater than that of the sample collected at the visits without gel dosing (No Gel/No Sex, No Gel/Sex visits).

This unique design allows each participant to serve as their own control for these comparisons.

We hypothesize that coitus and semen may not have the same impact on PK/PD in the setting of daily gel application due to continual accumulation of drug in cervicovaginal tissue over time. Thus Group 2 will compare PK/PD after 7 daily doses of gel in the absence of sex to that of the PK/PD after the couple engages in sex. While the 7-day dosing regimen is insufficient to establish steady-state tenofovir diphosphate concentrations for all women in cells and tissue (intracellular median half-life [interquartile range] 61 (49-112 hours in peripheral blood mononuclear cells [PBMC], possibly shorter in tissue)⁶, the concentrations in tissue and cells achieved will enable us to test the study hypotheses. Furthermore, longer dosing periods may yield less reliable data as participant adherence to study product use may vary over time.

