5.2 Inclusion Criteria

Men and women in Group 1 and Group 2 must meet the following criteria to be eligible for inclusion in the study:

1. Able and willing to provide the following:
 - a. Written informed consent to be screened for and take part in the study
 - b. Adequate locator information, as defined in site SOPs
2. Per participant report, at low risk for HIV/STI. Low risk is defined as:
 - a. No STIs in the 6 months prior to Screening
 - b. No non-therapeutic intravenous drug use in the 18 months prior to Screening
 - c. In a mutually monogamous relationship with a partner of the opposite sex for 6 months prior to Screening and the intent to stay in this relationship for the next 4 months
3. At Screening and Enrollment, both partners independently report not using barrier contraception and/or barrier protection as part of normal coital routine and report the intent to continue said sexual practice for the duration of study participation
4. HIV-uninfected based upon testing performed by study staff at Screening (per protocol algorithm)
5. Agrees not to participate in other research studies involving drugs, medical devices, or genital and rectal products, or large blood draw studies during study participation
6. Women must also meet the following criteria:
 - a. Age 21 through 46 years (inclusive) at Screening, verified per site SOPs
 - b. Pap result in the 12 calendar months prior to Screening consistent with Grade 0 according to the Female Genital Grading Table for Use in Microbicide Studies Addendum 1 to the DAIDS Table for Grading Adult and Pediatric Adverse Events, Version 1.0, December 2004 (Clarification dated August 2009), or satisfactory evaluation with no treatment required

of non-Grade 0 Pap result per American Society for Colposcopy and Cervical Pathology (ASCCP) guidelines in the 12 calendar months prior to the Screening Visit

Note: Women with a documented normal result within the 12 months prior to screening need not have a Pap smear during the screening period. Women with abnormal Pap smears can be enrolled upon completion of the initial phase of evaluation if no current treatment is indicated (based on local standard of care for management of abnormal cervical cytology). Need for a repeat Pap within 6 months does not preclude enrollment prior to that result becoming available.

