- c. Must be currently using effective non-barrier contraception, other than a contraceptive vaginal ring or intrauterine device, for at least three months prior to Screening (i.e., oral contraceptive, patch, injectable hormones, subdermal implants, female or male sterilization) and intending to use this method for the course of the study
- d. Per participant report, regular menstrual cycles with at least 21 days between menses (does not apply to participants who report using a progestin-only method of contraception at screening, e.g., Depo-Provera)

Note: This criterion is not applicable to participants using continuous combination oral contraceptive pills, as the absence of regular menstrual cycles is an expected, normal consequence in this context.

- e. Anatomy sufficient for performing pelvic examinations and for collecting vaginal and cervical specimens
- f. Female participants must also agree to abstain from intercourse (oral, anal, or penile-vaginal) and other vaginal practices (e.g., masturbation, douching, tampon use, application of lubricants/spermicides or other related practices) 72 hours prior to each follow-up visit. Group 2 participants must agree to also abstain from the aforementioned practices throughout the at-home gel use period

7. Men must also meet the following criteria:

- a. Age 21 or older at Screening, verified per site SOPs
- b. Agree to abstain from intercourse (oral, anal, or penile-vaginal) and other penile practices (e.g., masturbation, application of lubricants/spermicides or other related practices) 72 hours prior to each follow-up visit. Group 2 participants must also agree to refrain from intercourse (oral, anal, or penile-vaginal) throughout their partner's at-home gel use period

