6.9 Prohibited Medications and Practices

Concomitant use of prohibited non-study products (e.g., female use of lubricants) and other practices, including but not limited to intercourse (oral, anal, or penile-vaginal), masturbation, or other related practices 72 hours prior to each follow-up will be assessed. In addition, Group 2 female participants will be asked to refrain from these practices while dosing with gel at home and Group 2 male participants will be asked to refrain from engaging in intercourse during the at-home gel use period.

Participants will be counseled to avoid such use of the aforementioned products/practices when appropriate.

The use of immune modulators is prohibited. Participants requiring the use of these agents should not be included in the trial.

Participants are not expected to require gynecologic surgical procedures during follow-up; however, should such a procedure be required, the IoR/designee will consult the PSRT regarding ongoing product use by the participant.

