	Vaginal/ Cervical/ Penile	
 • Vaginal fluid pH • Rapid Trichomonas test • KOH wet mount for candidiasis, if indicated • Wet mount for BV, if indicated • Cervical specimen for pap smear, if indicated • CVL for PD

Note: The screening semen sample from the male partner will be used to assess the typical semen biomarker value for each male participant so that the volume of ejaculate can be assessed using the CVL. This data will inform any change in drug concentration or activity observed in the post-coital samples.

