7.3 Group 1 (Single Dose/BAT Cohort) – Enrollment and Study Follow-up Visits

Approximately 2-3 days after the final day of the female participants' menses (cessation of bleeding) following the Screening Visit, couples will return to the clinic for Visit 2 (Enrollment- No Gel/Coitus). Scheduling guidance for participants who are amenorrhoeic can be found in the SSP Manual. Participants will receive coital visit instructions which will include information regarding when participants should return to the study clinic (no more than 2 hours after completing the coital act) and other

information to ensure participants comply with study requirements. The couple will then engage in coitus at a local hotel or similar location. Female participants will return to the clinic after completing the coital act for post-Coitus sampling procedures at Visit 2b (Post-Coital Sampling).

Approximately 3-7 days following Visit 2b (Post-Coital Sampling), the couple will return for Visit 3a (Gel -1hr/Coitus). Female participants will be provided study product for application at the hotel or comparable location. Participants will receive coital visit instructions which will include information regarding the timing of study product application (1 hour prior to coitus), when participants should return to the study clinic (no more than 2 hours after completing the coital act), and other information to ensure participants comply with study requirements. Participants will insert the study product approximately 1 hour prior to coitus. Participants will then engage in coitus and female participants will return to the clinic no more than 2 hours after completing the coital act and undergo post-sex sampling procedures at Visit 3b (Post-Coital Sampling).

After a minimum 10-day washout period, females will return to the clinic for Visit 4a (Gel -1hr/ No Coitus), female participants insert a single dose of gel. Sampling procedures will occur at a similar time to those taken at Visit 3b (Post-Coital Sampling).

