Δ Visit 2a only, \blacksquare Visit 2a, 3a, 5a,7a only, \blacktriangle Visit 3a, 4a, 5a, 6a, 7a only

Table 8: Group 1- Visit 2b: Post-Coital Sampling, Visit 3b: Post-Coital Sampling, Visit 4b: Sampling, Visit 5b: Post-Coital Sampling, Visit 6b: Sampling

Group 1 Visit 2b: Post-Coital Sampling, Visit 3b: Post-Coital Sampling, Visit 4b: Sampling, Visit 5b: Post-Coital Sampling, Visit 6b: Sampling		
Component	Female Participant Procedures	
Administrative and Regulatory	
 • Provide reimbursement • Schedule next visit or contact, if indicated • Collect coitus visit data▣ 	
Clinical	
 • Record/update AEs • Perform pelvic exam 	
Behavioral/Counseling	
 • Conduct behavioral assessment▲ 	
Laboratory	Blood	
 • PK ▲
	Vaginal/Cervical	
 • Vaginal fluid pH • CVL 
 – PK▲ – PD – Semen biomarker▣ • Vaginal and cervical biopsies▲ 
 – PK • Cervical cytobrush▲ 
 – PK
	Rectal	
 • Rectal sponge▲ 
 – PK
Study Product Supply	
 • Collect used applicator/unused study product (if any)▲ 	

▣ Visit 2b, 3b, 5b only, ▲ Visit 3b, 4b, 5b, 6b only

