The difference in drug concentration levels at the visits where the female participants dose with gel and engage in coitus vs. the visits where female participants dose with gel and do not engage in coitus will be analyzed using the paired t-test or Wilcoxon signed-ranks test, as appropriate. In Group 1, for assessment of the BAT dosing regimen, DC from the visit where female participants perform BAT dosing with gel, coitus, and post-coitus gel will be compared to DC from the visit where female participants dose with gel (-1 hour) and do not engage in coitus. The BAT DC will also be compared to the visit where female participants dose with gel (-1 hour) and engage in coitus.

For each of the nine (9) assessments, the estimate of the mean percentage change along with the corresponding two-sided p-value and a 95% confidence interval will be presented. Significance level p-values will be adjusted for multiple comparisons using the FDR method.

In addition, change in amount (mass) of vaginal drug after dosing will also be assessed in CVL in similar fashion. As an explanatory variable, the screening semen sample from the male partner will be used to assess the typical semen biomarker value for each male participant so that the volume of ejaculate can be assessed using the CVL.

Primary Pharmacodynamic Analysis

In order to assess the impact of coitus (and semen) on pharmacodynamics (PD) of luminal drug by measuring the anti-HIV-1 activity in CVL samples, antiviral activity (percent inhibition) will be compared at various visits within each cohort. For Group 1, the difference in mean percent inhibition will be compared between:

1. No gel use with coitus vs. endogenous activity (baseline) (impact of coitus on endogenous activity)

For each group, and dose timing (-1 and -24 hours in Group 1 and -1 and -72 hours in Group 2), the difference in mean percent inhibition will be compared between:

2. Gel use alone vs. endogenous activity (baseline) (PD in absence of coitus)
3. Gel use with coitus vs. endogenous activity (baseline) (PD of product following coitus compared to baseline CVL activity)
4. Gel use alone vs. gel use with coitus (Difference in PD in the absence vs following coitus)
5. Gel use with coitus vs. no gel use with coitus (Group 1 only) (PD of product following coitus compared to post-coitus endogenous activity)

In Group 1, for assessment of the BAT dosing regimen, the difference in mean percent inhibition will be compared between:

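### The protocol does not require abstinence before the Screening CVL, so the no-gel/no-sex baseline behind several primary PD comparisons may contain recent coitus, undetected

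*Protocol*

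**What the plan says.** **Abstinence rule.** Section 5.2 (items 6f and 7b) asks women and men to refrain from intercourse and listed practices, "or other related practices) 72 hours prior to each follow-up visit". Section 6.7 counsels to the same window. Section 6.9 says that practices "72 hours prior to each follow-up will be assessed".

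**Baseline sample.** Section 2.1 relies on "CVL obtained at the Screening visit (no gel/no sex") for baseline data without product. Tables 6 and 11 place this CVL at Visit 1 in both groups and list PD as its only assay.

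**Population.** At Screening and Enrollment, "both partners independently report not using barrier contraception and/or barrier protection as part of normal coital routine" (Section 5.2, item 3).

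**Use in the analysis.** Section 10.6.2 makes this sample the reference for PD comparison 1, "No gel use with coitus vs. endogenous activity (baseline) (impact of coitus on endogenous activity"). It is also the reference for comparisons 2 and 3 and the first BAT comparison.

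**Detection.** In Group 1, Table 8 restricts the CVL semen biomarker to "Visit 2b, 3b, 5b only", and Table 9 adds Visit 7b. The behavioural assessment, which under Section 7.9 covers prohibited practices, first appears at Visit 2a (Group 1) or Visit 2 (Group 2).

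**The concern.** Section 2.1 argues that results can be interpreted only if sex and gel are both controlled, and that intercourse may itself change endogenous antiviral activity. Visit 1 carries a no-sex label, but no criterion or procedure makes the label true. A couple who had sex the previous evening would comply fully with the protocol.

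Comparison 1 would then set coitus against a mixture of no coitus and recent coitus. If the residual effect has the same direction as the effect at about 2 hours, the estimate is pulled toward zero. In comparisons 2 and 3 and the first BAT comparison, the reference is no longer the condition it is named for; the direction of bias there depends on how coitus changes endogenous activity. Group 2 has no no-gel/coitus visit, so this CVL is its only gel-free reference. Without a biomarker result or a record of last intercourse, affected baselines could not be identified at analysis.

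**Working it through.** **Step 1: does the rule reach Visit 1 or Visit 2a?** Screening has its own sections (7.2 and 7.4), and consent precedes any screening procedure. Section 7.3 is headed "Enrollment and Study Follow-up Visits", which names Enrollment apart from follow-up. On the wording, Visit 1 is outside the rule and Visit 2a is doubtful. Visit 2b, which follows 2a, is the other arm of comparison 1.

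**Step 2: which analyses use the baseline?**

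| Analysis (Section 10.6.2) | Uses Visit 1 CVL? |
|---|---|
| PD comparisons 1, 2, 3 | Yes |
| BAT PD comparison 1 | Yes |
| PD comparisons 4, 5 | No |
| BAT PD comparisons 2, 3, 4 | No |
| PK concentration contrasts | No |

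**Step 3: how often might coitus precede the sample?** The documents give no coital frequency. Assume r acts per week with Poisson timing. The chance of at least one act in the prior d days is 1 − exp(−r·d/7).

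| Window | r = 1 | r = 2 | r = 3 |
|---|---|---|---|
| 72 h (d = 3) | 35% | 58% | 72% |
| 24 h (d = 1) | 13% | 25% | 35% |
| 12 h (d = 0.5) | 7% | 13% | 19% |

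These are chances of exposure. They equal the attenuation of comparison 1 only if the full post-coital effect lasts the whole window and then stops. As a smooth alternative, suppose the effect of the latest act fades exponentially with a 12-hour half-life. With daily rate ρ = r/7 and k = ln 2/0.5 = 1.386 per day, mean attenuation is ρ/(ρ + k):
- r = 1: 0.143/1.529 = 9%
- r = 3: 0.429/1.815 = 24%

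The half-life is also an assumption.

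**Step 4: consequence for comparison 1.** First, the plan's own figure. Section 10.4.2 gives power 0.565 for a 10-point difference with N = 20 and SD 20. A two-sided 5% paired t-test (noncentral t, 19 df) returns 0.565, and all ten rows of Table 19 reproduce. The 5% level is assumed because Section 10.4 does not state it.

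The plan computed that power for gel with coitus versus gel alone, so using SD 20 for comparison 1 is a borrowing. Let a share f of baselines carry the full coital effect Δ. The expected difference becomes (1 − f)Δ, and the SD becomes √(400 + f(1 − f)Δ²). For Δ = 10 and f = 0.25, these are 7.5 and √418.75 = 20.46.

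| True Δ (points) | f = 0 | f = 0.10 | f = 0.25 | f = 0.50 |
|---|---|---|---|---|
| 10 | 0.565 | 0.472 | 0.344 | 0.178 |
| 14 | 0.844 | 0.744 | 0.569 | 0.289 |
| 20 | 0.989 | 0.955 | 0.831 | 0.476 |

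The plan's stated power figures are not in dispute. The table shows only how comparison 1 would respond to a given f.

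**The case against.** Several stronger readings are tempting, and the documents do not support them.

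- **Abstinence could not have been requested.** It could. Section 7.1 lets staff explain the study before Visit 1, Sections 7.2 and 7.4 allow screening over several visits, and Section 13.5 makes abstinence before study visits a consent topic. The SSP Manual and the sample consent forms, not available here, may say more. None of the text shown makes it a requirement for the baseline CVL.
- **Every later CVL is taken under abstinence.** This is not established, because Enrollment may fall outside the rule.
- **Douching and vaginal products are equally uncontrolled.** Exclusion 7c bars douches and other intravaginal products (tampons excepted) for 30 days before Enrollment, and Screening is at most 30 days before Enrollment. Only a Screening held about 27 to 30 days ahead leaves part of the prior 72 hours uncovered. The gap is essentially intercourse.
- **Detection is ruled out.** Appendices I and II mark Visit 1 in a combined CVL row for PK, PD and/or semen biomarker. That row is generic, and the detailed tables list PD alone, so detection is unplanned rather than impossible.
- **Comparison 1 loses 35–72% of its effect.** That range is a ceiling on exposure. The protocol samples at about 2 hours and says nothing on persistence to 72 hours.
- **The semen calibrator is biased.** "The screening semen sample from the male partner will be used to assess the typical semen biomarker value for each male participant", and it too is collected without the abstinence asked before follow-up visits. The documents do not say that abstinence length changes the biomarker, and Section 10.6.2 uses it only as an explanatory variable.

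The strongest defence is scope: the only PD contrast with a power calculation is gel with coitus versus gel alone, which does not use this baseline. That stands, and it limits the point without removing it.

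**Conclusion.** The concern holds in a limited form. As written, the protocol allows recent coitus before the sample it calls no gel/no sex and has no plan to detect it. The affected analyses are primary PD comparisons 1, 2 and 3 and the first BAT comparison. For comparison 1 the bias is toward zero, provided any lingering effect has the same direction as the effect at about 2 hours.

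The documents cannot fix the size. The exposure ranges rest on assumed coital rates, and the attenuation rests further on an assumed duration of effect. A reader might infer that the trial's central question is compromised. It is not: the direct coitus contrasts in PD and PK do not depend on this baseline. The point still merits correction before enrolment, because this is a rule about collection and analysis cannot recover the missing information afterwards.

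**What to change.** 1. Reword Sections 5.2 (6f and 7b), 6.7 and 6.9 so that the 72-hour rule applies before baseline CVL collection, Enrollment and each follow-up visit. Apply it through instruction at pre-screening, or by taking the baseline CVL at a second screening visit after consent, which Sections 7.2 and 7.4 already allow.
2. Record time since last intercourse when the baseline CVL is taken.
3. Add the semen biomarker to the Visit 1 CVL in Tables 6 and 11, so that contaminated baselines can be identified. The assay is already planned; Table 15 lists it at Visit 9, which involves no coitus.
4. Collect the male semen sample under the same abstinence. This is a consistency step with no documented effect size.

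The cost is a wording change, a second short screening visit for some couples, one recorded item and one more assay on an existing specimen.

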5.3 Exclusion Criteria

Men and women who meet any of the following criteria will be excluded from the study. Previous participation in Group 1 or Group 2 of the MTN-011 clinical trial is not exclusionary.

1. Participant report of any of the following:
 - a. Known allergy to the study product (ever)
 - b. Post-exposure prophylaxis (PEP) for HIV exposure within 6 months prior to Screening
 - c. Participation in any other research study involving drugs, medical devices, or genital products 30 days or less prior to Enrollment
 - d. Plans to relocate away from the study site in the next 4 months
 - e. History of domestic violence with current partner (ever)
 - f. Systemic or topical antimicrobials within the last 7 days prior to Enrollment
 - g. Currently using or planning to use pharmacologic immune modulator(s)

2. At Screening or Enrollment, symptomatic urinary tract infection (UTI)

Note: Otherwise eligible participants diagnosed with UTI during screening are offered treatment and may be enrolled after completing treatment and all symptoms have resolved as long as treatment is completed and all symptoms have resolved within 30 days of obtaining informed consent for Screening/Enrollment.

3. At Screening, has a positive hepatitis B surface antigen (HBsAg) test result
4. At Screening or Enrollment, has an STI or reproductive tract infection (RTI) requiring treatment per current CDC guidelines
5. Genital signs and/or symptoms of Grade 2 or higher

Note: For female participants, cervical bleeding associated with speculum insertion and/or specimen collection judged to be within the range of normal according to the clinical judgment of the IoR/designee is considered expected non-menstrual bleeding and is not exclusionary.

Note: Otherwise eligible participants with exclusionary genital findings may be enrolled after the findings have improved to a non-exclusionary severity grading or resolved as long as treatment is completed and all symptoms have resolved within 30 days of obtaining informed consent for Screening/Enrollment.

6. Has any other condition that, in the opinion of the IoR/designee, would preclude informed consent, make study participation unsafe, complicate interpretation of study outcome data, or otherwise interfere with achieving the study objectives

7. Women who meet any of the following criteria will be excluded from the study:

a. Participant report (or clinical finding) of the following:

i. Last pregnancy outcome 90 days or less prior to Enrollment

ii. Currently pregnant

Note: Self-reported pregnancy is adequate for exclusion from the study. A documented negative pregnancy test performed by study staff is required for inclusion.

iii. Currently breastfeeding

iv. Intends to become pregnant in the next 4 months

v. Gynecologic or genital procedure (e.g., tubal ligation, dilation and curettage) within the prior 30 days to Enrollment

Note: This does not include biopsy for the evaluation of an abnormal pap result or endometrial biopsy that occurred more than 7 days prior to Enrollment.

b. Any of the following laboratory abnormalities at Screening:

i. Hemoglobin less than 10.0 g/dl

ii. Platelet count less than 100,000/mm³

Note: Otherwise eligible participants with an exclusionary test may be re-tested during the screening process

c. Use of a vaginal douche or other intravaginal products (excluding tampon use) in the 30 days prior to Enrollment

d. Currently menopausal or perimenopausal

8. Men who meet any of the following criteria will be excluded from the study:

a. Participant report of penile procedures (e.g. biopsy, circumcision) within 42 days prior to Enrollment

b. For uncircumcised men, per participant report, treatment of candidal balanoposthitis/ balanitis within 30 days prior to Enrollment

